Table ITSD.5.	Summary of Basal Insulin Adjustments after Hypoglycemia Assessment	34
Table ITSD.6.	Prandial Insulin Doses and Corresponding Self Monitored Blood Glucose Values Pattern Adjustment Plan	36
Table ITSD.7.	LY900014 or Insulin Lispro Adjustment Algorithm Pattern Adjustment Plan	36
Table ITSD.8.	Concomitant Medications	39
Table ITSD.9.	Insulin to Carbohydrate Ratio for Determining the Prandial Insulin Dose for the Mixed-Meal Tolerance Test: For Use with Patients Who Use Pattern Adjustment to Determine Prandial Insulin Doses	46

List of Figures

Figure		Page
Figure ITSD.1.	Illustration of study design for Clinical Protocol I8B-FH-ITSD	23

List of Appendices

Appendix		Page
Appendix 1.	Abbreviations and Definitions	63
Appendix 2.	Clinical Laboratory Tests	67
Appendix 3.	Study Governance Considerations.	68
Appendix 4.	Hepatic Monitoring Tests for Treatment-Emergent Abnormality	72
Appendix 5.	World Health Organization Classification for Diabetes	73
Appendix 6.	New York Heart Association Cardiac Disease Classification	74
Appendix 7.	Classification of Contraceptive Methods	75

1. Synopsis

Title of Study:

A Prospective, Randomized, Double-Blind Comparison of LY900014 to Insulin Lispro, in Combination with Insulin Glargine or Insulin Degludec in Adults with Type 1 Diabetes

Rationale:

A prandial insulin with faster-onset and/or faster-offset characteristics might reduce glycemic excursions and the incidence of delayed postprandial hypoglycemia compared to currently available rapid-acting insulin analogs. Rapid-acting insulins, such as Humalog®, have been shown to have a more rapid onset of action compared to human insulin; however, the general consensus is that they are not rapid enough to match carbohydrate absorption, whether delivered by pump or syringe/pen injector, thereby limiting efficacy. An ultra-rapid-acting prandial insulin that shifts the pharmacokinetic (PK) and glucodynamic profiles of insulin to provide an even faster onset of action would better match carbohydrate absorption and allow for efficacious dosing immediately prior to meals or even after meals. Ultra-rapid insulin (URI) could be useful in the treatment of type 1 diabetes (T1D) and type 2 diabetes (T2D) in adults and children when delivered by multiple daily injections (MDI) or by continuous subcutaneous insulin infusion (CSII).

The aim of this study is to demonstrate that an ultra-rapid formulation of insulin lispro, LY900014, is noninferior to insulin lispro on glycemic control as measured by change from baseline to Week 26 in hemoglobin A1c (HbA1c) in patients with T1D when administered in a double-blind manner as prandial insulin in combination with basal insulin glargine or insulin degludec in accordance with local regulations.

Objectives/Endpoints:

Objectives	Endpoints
Primary Objective	
To test the hypothesis that LY900014 is noninferior to insulin lispro on glycemic control (non-inferiority margin [NIM]=0.4% for HbA1c) in patients with T1D when administered as prandial insulin (0 to 2 minutes prior to the meal), in combination with basal insulin glargine or insulin degludec for 26 weeks	[1] Difference between LY900014 and insulin lispro in change from baseline to Week 26 in HbA1c
Multiplicity-Adjusted Objectives	
To test the hypothesis that LY900014 is superior to insulin lispro in controlling 1-hour postprandial glucose (PPG) excursions when administered as prandial insulin	[2] Difference between LY900014 and insulin lispro in the 1-hour PPG excursion (serum glucose measured 1 hour after the start of the meal minus fasting serum glucose) from a mixed-meal tolerance test (MMTT) at Week 26
To test the hypothesis that LY900014 is superior to insulin lispro in controlling 2-hour PPG excursions when administered as prandial insulin	[3] Difference between LY900014 and insulin lispro in the 2-hour PPG excursion (serum glucose measured 2 hours after the start of the meal minus fasting serum glucose) from an MMTT at Week 26
To test the hypothesis that LY900014 is superior to insulin lispro on improving glycemic control (HbA1c) when administered as prandial insulin	[4] Difference between LY900014 and insulin lispro in change from baseline to Week 26 in HbA1c

Other Secondary Objectives	
[5] To compare LY900014 and insulin lispro with respect to the rate of severe hypoglycemic events	[6] Rate (events/patient/100 years) of severe hypoglycemic events from baseline through Week 26
[7] To compare LY900014 and insulin lispro with respect to the incidence and rate of documented symptomatic postmeal hypoglycemia	[8] Rate (events/patient/year and/or events/patient/30 days) and incidence (percent of patients with at least 1 event) of documented symptomatic postmeal hypoglycemia within 1 and 2 hours after start of a meal from Week 12 through Week 26 and Week 0 through Week 26
[9] To compare LY900014 and insulin lispro with respect to the incidence and rate of documented symptomatic hypoglycemia	[10]Rate (events/patient/year and/or events/patient/30 days) and incidence (percent of patients with events) of documented symptomatic hypoglycemic events from Week 12 through Week 26 and Week 0 through Week 26
[11]To compare LY900014 and insulin lispro with respect to 1,5-Anhydroglucitol (1,5-AG)	[12]Change from baseline in 1,5-AG values at Week 26
[13]To compare LY900014 and insulin lispro with respect to 10-point self-monitored blood glucose (SMBG) profiles	[14]Change from baseline in 10-point SMBG values at Week 26
[15]To compare LY900014 and insulin lispro with respect to total, basal, and prandial insulin dose	[16] Change from baseline in total, basal and prandial insulin doses and prandial/total insulin dose ratios at Week 26
[17]To compare LY900014 and insulin lispro with respect to the proportion of patients achieving HbA1c targets	[18]The proportion of patients with HbA1c <7% and ≤6.5% at Week 26

Summary of Study Design:

Study I8B-FH-ITSD is a Phase 3, prospective, randomized, double-blind, outpatient, multinational, multicenter 2-treatment group, parallel, active-controlled study conducted in patients with T1D currently using an MDI regimen OR premixed insulin with at least 2 injections daily.

Treatment Groups and Duration:

The study includes a 1-week screening period and an 8-week lead-in period. In the 2 treatment groups, LY900014 and insulin lispro will be administered immediately (0-2 minutes) prior to each meal in a double-blind manner. Patients will complete a 26-week treatment period and a 4-week safety follow-up period.

Number of Patients:

Approximately 438 participants will be screened to achieve 350 randomized patients and 298 patients completing 26 weeks of treatment. Approximately 280 Chinese patients will be randomized. The other 70 randomized patients are planned to be from other countries, which may include Mexico, Argentina, Brazil, India and Ukraine. The final participating countries and allocated patient numbers will be adjusted based on the actual condition.

Statistical Analysis:

The primary analysis is for the treatment period through Week 26.

Efficacy analyses will be conducted on all randomized patients using an intention-to-treat (ITT) approach according to the treatment the patients are assigned. The analyses for the primary and multiplicity-adjusted objectives will include data collected prior to permanent discontinuation of investigational product (IP) through Week 26. When change from baseline is included as a response variable of analysis models, the patient will be included in the analysis only if a baseline and at least 1 post-baseline measurement are available. Selected efficacy analyses will also be conducted using the Per Protocol (PP) and Completer populations.

Safety analyses will be conducted on the Safety population. Analyses of adverse events (AEs) will include 2 sets of analyses, unless otherwise specified. The first set of analyses will include data collected prior to permanent discontinuation of IP. The second set of analyses will include all data collected during the course of the entire study regardless of IP use. Analyses of hypoglycemia will be conducted on data collected prior to permanent discontinuation of IP, while analyses for post-treatment may be conducted as needed. Analyses of safety laboratory measurements will be performed on all data collected during the planned treatment period regardless of IP use. Week 26 analyses will include treatment comparisons between two treatment groups.

Baseline is defined as the last nonmissing measurement at or before the randomization visit (Visit 8), unless otherwise specified.

The primary efficacy comparison will be based on the contrast between LY900014 and insulin lispro at Week 26 (Visit 18) from the mixed-effect model repeated measure (MMRM) analysis of change from baseline in HbA1c using all randomized patients. If the upper limit of the 2-sided 95% confidence interval (CI) for the least squares (LS) mean difference in the change from baseline in HbA1c for LY900014 minus insulin lispro is below +0.4%, LY900014 will be declared noninferior to insulin lispro. The model for this analysis will include the fixed class effects of treatment, strata (country, type of basal insulin, and metformin use at study entry), visit, and treatment-by-visit interaction, as well as the continuous, fixed covariate of baseline value.

A graphical approach (Bretz et al. 2011) for multiple comparisons will be used to strongly control the overall Type I error (2-sided alpha level of 0.05) for testing the treatment effect for the primary and the following multiplicity-adjusted objectives: superiority of LY900014 compared with insulin lispro for 1-hour PPG excursion at Week 26, 2-hour PPG excursion at Week 26, and change from baseline to Week 26 in HbA1c.

An analysis of covariance (ANCOVA) model with strata (country, type of basal insulin, baseline HbA1c strata [≤8.5%, >8.5%], and metformin use at study entry), and treatment as fixed effects and baseline as a covariate will be used to analyze the 1-hour and 2-hour PPG excursions. However, if the percentage of the patients with missing MMTT data at baseline is higher than 15%, a constrained longitudinal data analysis model (Liu et al. 2009; Lu 2010) will be used instead. Analyses details will be documented in the statistical analysis plan (SAP).

Hypoglycemia rates will be summarized for periods of 30 days, 1 year, and 100 years (severe hypoglycemia only). The rate of severe hypoglycemia per 100 years will be compared between treatment groups using the empirical method. For each of the other categories of hypoglycemia, the number of hypoglycemia events during a specific period (rate) after randomization (for example, 0-12 weeks of treatment period) will be analyzed by using a negative binomial regression model. The model will include treatment and the baseline hypoglycemia rate (measured during lead-in) as a covariate. An offset defined as the log transformation of treatment exposure in the specific period

(days)/365.25 days (or 30 days) will be included in the model to estimate the rate of hypoglycemia per year (or per 30 days). The proportion of patients with at least 1 hypoglycemic event in each category (incidence) during a specific period after randomization will be analyzed using a logistic regression model including treatment and baseline hypoglycemia rate value in the model.

Continuous safety variables, as well as the change from baseline for these variables, will be analyzed by MMRM or ANCOVA models. For categorical variables, Fisher's exact test will be used to compare treatment groups unless otherwise specified.

Change from baseline to last-observation-carried forward endpoints for the European Quality of Life – 5 Dimensions 5 Level (EQ-5D-5L), Insulin Treatment Satisfaction Questionnaire (ITSQ), and Work Productivity and Activity Impairment Questionnaire General Health (WPAI-GH) will be analyzed using ANCOVA models.

References:

- Lu K. On efficiency of constrained longitudinal data analysis versus longitudinal analysis of covariance. *Biometrics*. 2010;66(3):891-896.

2. Schedule of Activities

Study Procedure	Study Screening		Lead-In Period						In	tensi	ve Ti	tratio	n Per	riod		intena Perio		Safety Follow-Up	ED	
													 							
eCRF Visit Number	1	2	3a	4a	5	6a	7	8	9a	10	11	12a	13	14a	15	16	17	18	801	EDp
Visit Window (± days)		3	3	3	3	3	3	4	3	3	7	7	7	7	7	7	7	7	7	
Time on Study Relative to First Active	-9	-8	-7	-6	-4	-2	-1	0	1	2	4	6	8	10	12	18	22	26	30	
Treatment Dose (weeks)																				
Informed consent signed	X																			
IWRS	X	X	X	X	X	X	X	X	X	X	X	X	X	X	X	X	X	X	X	X
Patient eligibility review	X																			
Randomization ^c								X												
Clinical Assessments																				
Patient demographics	X																			
Medical history and preexisting conditions	X																			
Physical exam/height ^d	X																			
Concomitant medication	X	X	X	X	X	X	X	X	X	X	X	X	X	X	X	X	X	X	X	X
Adverse events and product complaints	X	X	X	X	X	X	X	X	X	X	X	X	X	X	X	X	X	X	X	X
Body weight ^e	X	X			X		X	X		X	X		X		X	X	X	X	X	X
Vital signs: blood pressure/pulse ratef	X	X			X		X	X		X	X		X		X	X	X	X	X	X
ECG (12-lead; local)	X																			
Diabetes and nutrition counselingg		X																		
Transfer to insulin lisproh		X																		
Transfer to allowed study basal insulin		X																		
regimeni																				
Basal and prandial insulin dose assessment		X	X	X	X	X	X	X	X	X	X	X	X	X	X	X	X	X		
Titrate basal insulin		X	X	X	X	X	X													
Titrate prandial insulink								X	X	X	X	X	X	X	X					

Page 13

Study Procedure	Study Screening		Lead-In Period						In	itensi	ve Ti	tratio	n Per	iod		ainten Perio		Safety Follow-Up	ED	
												Tre	atme	nt Per	iod					
eCRF Visit Number	1	2	3a	4a	5	6a	7	8	9a	10	11	12a	13	14a	15	16	17	18	801	EDp
Visit Window (± days)		3	3	3	3	3	3	4	3	3	7	7	7	7	7	7	7	7	7	
Time on Study Relative to First Active	-9	-8	-7	-6	-4	-2	-1	0	1	2	4	6	8	10	12	18	22	26	30	
Treatment Dose (weeks)																				
Ancillary Supplies/Diaries/IP																				
Dispense blood glucose meter and ancillary		X						X		X	X		X		X	X	X	X		
supplies and complete trainingl,m								 												
Dispense study diary		X			X		X	X		X	X		X		X	X	X	X		
Diary use training ^m		X																		
Collect Study Diary and Transfer Diary Data to eCRF (InForm) ⁿ					X		X	X		X	X		X		X	X	X	X	X	X
Train on collecting 4- and 10-point SMBG profiles ^m		X																		
Review 4-point SMBG profiles ^o			X	X	X	X	X	X	X	X	X	X	X	X	X	X	X	X	X	X
Remind patient of 10-point SMBG requirementsp						X	X							X			X			
Review 10-point SMBG profiles								X							X			X		Χq
Review/discuss hypo data			X	X	X	X	X	X	X	X	X	X	X	X	X	X	X	X		X
Dispense IP		X			X			X			X		X		X	X	X			
Patient returns used and unused study drug supplies					X			X			X		X		X	X	X	X		X
Drug accountability					X			X			X		X		X	X	X	X		X
Laboratory Assessments													•					1	1	.1
Patient fasts prior to visit		X						X										X		X
MMTT ^r								X										X		
Urinalysis panel	X																			
Pregnancy test ^S	X							X												
Follicle-stimulating hormone test ^t	X																			
Chemistry panel	X							X										X		X
Fasting serum glucose		X																		
Hematology	X							X										X		X

Study Procedure	Study Screening	Lead-In Period					Intensive Titration Period									intena Period		Safety Follow-Up	ED	
												Trea	tme	nt Per	iod					
eCRF Visit Number	1	2	3a	4a	5	6a	7	8	9a	10	11	12a	13	14a	15	16	17	18	801	EDp
Visit Window (± days)		3	3	3	3	3	3	4	3	3	7	7	7	7	7	7	7	7	7	
Time on Study Relative to First Active	-9	-8	-7	-6	-4	-2	-1	0	1	2	4	6	8	10	12	18	22	26	30	
Treatment Dose (weeks)																				
1,5-Anhydroglucitol								X			X				X			X		X
Hemoglobin A1c	X						X	X			X		X		X			X	X	X
Lipid profile								X										X		X
Anti-insulin lispro antibodies		X						X		X	X				X			X	X	X
Health Outcomes Questionnaires ^u																				
EQ-5D-5L		X						X										X		X
ITSQ		X						X										X		X
WPAI-GH		X						X										X		X

Abbreviations: ECG = electrocardiogram; eCRF = electronic case report form; ED = early discontinuation; EQ-5D-5L = European Quality of Life – 5 Dimensions 5 Level;; hypo = hypoglycemia; IP = investigational product; ITSQ = Insulin Treatment Satisfaction Questionnaire; IWRS = interactive web response system; MMTT = mixed-meal tolerance test; SMBG = self-monitored blood glucose; WPAI-GH = Work Productivity and Activity Impairment Questionnaire General Health.

- ^a Telephone visits are indicated by shaded columns. Activities include:
 - Record visit in the IWRS.
 - Collect adverse events and concomitant medications.
 - Review blood glucose readings and study drug doses.
 - Adjust prandial insulin or basal insulin doses as needed.
 - Review hypoglycemic events.
 - Provide reminders regarding scheduled visits, fasting, and SMBG profiles, as applicable.
- b Patients who have been randomized will be asked to return for the ED visit in a fasting state unless patient is already fasting and at the site when the decision to discontinue is made. Patients who discontinue during the lead-in period prior to randomization, and who are not already at the site, will be asked to return for the ED in a nonfasting state and all activities should be completed except for laboratory tests and questionnaires (ITSQ, EQ-5D-5L, and WPAI-GH).
- c Randomization should occur after all Visit 8 procedures including MMTT. If MMTT is rescheduled post Visit 8, randomization should not occur until baseline MMTT is completed. The patient will administer their first dose of study insulin with the first meal after the MMTT has been completed and randomization has occurred.
- d Physical examination shall be performed at Visit 1. It shall be performed at other visits if deemed necessary by the investigator.
- e Patients should be advised to remove their shoes and empty their pockets before the body weight is obtained.

f Vital sign measurements must be taken before obtaining an ECG tracing and before collection of blood samples for laboratory testing. These measurements should be determined after patients have been seated quietly for at least 5 minutes in a chair with feet on the floor. The arm used for blood pressure measurement should be supported at heart level.

- g Initial training at Visit 2 will include diabetes education and nutrition counseling. Appropriate site personnel will administer training and education using locally approved diabetes education/training materials or other materials provided by the Sponsor. Patients may be provided abbreviated training and education at visits following Visit 2 as appropriate.
- h Only applies to patients taking insulin glulisine, insulin aspart, or regular human insulin.
- Patients will be transferred to a study basal insulin regimen at Visit 2. Investigators will determine the appropriate basal insulin regimen for each patient. It is expected that most of the basal insulin dose adjustments should occur during the lead-in period. However, basal insulin titration may continue during the intensive titration period for patients who need more intensification to achieve glycemic targets. Basal insulin dose adjustments during the maintenance period should be made for safety reasons such as hypoglycemia and unacceptable hyperglycemia.
- Assessments of the basal insulin dose should be made, at minimum, weekly during the lead-in period, including Weeks -5 and -3. Assessment of the prandial insulin dose should be made, at minimum, weekly during the initial 12 weeks after randomization, including Weeks 3, 5, 7, 9, and 11.
- k During the lead-in period, prandial doses, correction factors, and insulin to carbohydrate ratios should be evaluated and adjustments should be made for safety reasons such as hypoglycemia and unacceptable hyperglycemia. During the intensive titration period, prandial insulin dose should be adjusted in order to meet the target SMBG levels. Further adjustments during the maintenance period should be made for safety reasons such as hypoglycemia and unacceptable hyperglycemia.
- Glucose monitoring supplies will be dispensed at other visits, as needed.
- m Training may be repeated at other visits, as needed.
- ⁿ Study sites will retain study diaries.
- Patients should be encouraged to measure a minimum of 4 SMBG readings daily to satisfy dose titration. 4-point SMBG is required on three nonconsecutive days before each visit.
- P Patients in both study arms should be instructed to perform three 10-point SMBG profiles during a 2-week period. The 10-point profile is completed over a 1-day period, preferably on 3 nonconsecutive days (weekdays and weekends). Ten-point SMBG profiles should not be performed on the day of MMTT.
- 9 Review of 10-point SMBG profiles at the ED visit will take place only for patients randomized into the study.
- r MMTT can occur 0 to 4 days prior to the visit, and patient must be fasting prior to start of the MMTT. Time 0 of the MMTT will be when the patient starts to consume the meal. Serial venous blood samples to measure serum glucose will be taken at time -15, 0, 15, 30, 60, 120, 180, and 240 minutes after the start of the meal.
- s Serum pregnancy test that is analyzed by central laboratory must be performed in women of childbearing potential at Visit 1 followed by a local urine or serum pregnancy test within 24 hours prior to IP exposure at randomization (Visit 8) and at other times at the investigator's discretion. When required per local regulations and/or institutional guidelines, local pregnancy testing will occur at mandatory times during the study treatment period, and the local pregnancy test must be kept at site.
- Follicle-stimulating hormone test must be performed at Visit 1 for a postmenopausal woman who is between 50 and 54 years of age (inclusive) with an intact uterus, not on hormone therapy, and who has had at least 6 months of spontaneous amenorrhea.
- u Health outcomes questionnaires will be administered at the study sites based on the availability of appropriate translations. The questionnaires should be administered prior to other study procedures except at Visit 8 and Visit 18 when questionnaires may be administered following the start of the MMTT.

3. Introduction

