7.2. Method of Treatment Assignment

Patients who meet all criteria for enrollment will be randomized to double-blind treatment at Visit 8. Assignment to treatment groups will be determined by a computer-generated random sequence using an interactive web-response system (IWRS). Patients will be randomized to 1 of the 2 treatment groups in a 1:1 ratio. Stratification will be by country (China vs. Other), HbA1c stratum (≤8.5% vs. >8.5% at Visit 7), type of basal insulin during the lead-in period (glargine U-100 vs. degludec U-100), and use of metformin at study entry (yes vs. no).

The IWRS will be used to assign all IP during the study, including insulin lispro during the lead-in period. The IWRS will be used to assign prefilled pens containing double-blind IP to each patient randomized to the 2 blinded treatment groups. Site personnel will confirm that they have located the correct prefilled pens by entering a confirmation number found on the prefilled pens into the IWRS.

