Hypoglycemia rates will be summarized for periods of 30 days, 1 year, and 100 years (severe hypoglycemia only). The rate of severe hypoglycemia per 100 years will be compared between treatment groups using the empirical method (details will be described in the SAP). For each of the other categories of hypoglycemia, the number of hypoglycemia events during a specific period (rate) after randomization (for example, Weeks 0-12 of treatment period) will be analyzed by using a negative binomial regression model. The model will include treatment and the baseline hypoglycemia rate (measured during lead-in) as a covariate. An offset defined as the log transformation of treatment exposure in the specific period (days)/365.25 days (or 30 days) will be included in the model to estimate the rate of hypoglycemia per year (or per 30 days). The proportion of patients with at least 1 hypoglycemic event in each category (incidence) during a specific period after randomization will be analyzed using a logistic regression model including treatment and baseline hypoglycemia rate value in the model.

Continuous safety variables, as well as the change from baseline for these variables, will be analyzed by MMRM or ANCOVA models. For categorical variables, Fisher's exact test will be used to compare treatment groups unless otherwise specified. The analyses for assessing immunogenicity data will be described in the SAP.

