Appendix 1. Empirical Estimation of Relative Event Rate		

## 3. Revision History

Statistical analysis Plan (SAP) Version 1 was approved prior to the first patient visit. Version 1 was based on the Protocol I8B-FH-ITSD (ITSD) approved on 13 July 2018.

The main changes of the second version are listed below.

- Analysis period of from randomization to Week 26 (including all data regardless of IP use) was added for some of the safety analysis.
- Removed the baseline rate covariate from all hypoglycemia models as there were many critical outliers leading to inaccurate in the LSM and the biases were inconsistent.
- Summaries of postmeal hypoglycemia < 54 mg/dL were added.
- Summaries of postmeal hypoglycemia occurring >4 hours after start of a meal were added.
- COVID-19 related analyses were added.
- Summaries of pre-study insulin treatment type between treatment groups were added.
- The graphical testing scheme has been revised according to the simulation and optimization analysis results.

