#### 6.2. Adjustments for Covariates

Stratification will be by country (China vs. Other), HbA1c stratum ( $\leq 8.5\%$  vs. >8.5% at baseline), type of basal insulin during the lead-in period (glargine U-100 vs. degludec U-100), and use of metformin at study entry (yes vs. no). Stratification factors will be entered into the IWRS for randomization and also collected in the database by electronic case report form (eCRF) or central laboratory. The analysis models for efficacy endpoints will use the stratification factors as collected in the database.

For continuous analyses of HbA1c, the stratification factor of HbA1c stratum (baseline) will not be included. Instead, the continuous value of baseline HbA1c will be included in the analysis models.

Other analyses will include the stratification factors as noted in Sections 6.11 and 6.12.

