#### **I8B-MC-ITSD Statistical Analysis Plan Version 2**

Endpoint	Analysis Period	Statistical Method
Incidence of hypoglycemic events All Documented a Nocturnal a Documented Symptomatic a Non-Nocturnal (or Daytime) (Documented and between waking and bedtime) a	0-12, 0-26, 12-26 weeks	Logistic regression with treatment as an independent variable.
Rate of postmeal hypoglycemic events (per patient per 30 days / year) for all 3 main meals Documented Symptomatic a	$\leq 0.5, \leq 1, \leq 2, \leq 4, >1$ to $\leq 2, >2$ to $\leq 4$ and >4 hours after start of a meal within 0-12, 12-26, 0-26 weeks	Negative binomial regression with treatment, and log (exposure/30 days or exposure/365.25 days) as the offset in the model.
Incidence of postmeal hypoglycemic events for all 3 main meals Documented Symptomatic a	$\leq 0.5, \leq 1, \leq 2, \leq 4, >1$ to $\leq 2, >2$ to $\leq 4$ and >4 hours after start of a meal within 0-12,12-26, 0-26 weeks	Logistic regression with treatment as an independent variable.
Rate of severe hypoglycemic events (per patient per year / 100 years)	0-12, 0-26, 12-26 weeks	Exposure adjusted rate per year / 100 years (calculated by total number of events divided by total exposure for individual patients) will be provided and the empirical method (see 0 for details) will be used for treatment comparison.

Endpoint	Analysis Period	Statistical Method
Incidence of severe hypoglycemic	0-12, 0-26, 12-26 weeks	Proportion of patients with severe
events		hypoglycemia will be reported. The
		treatment comparison will be based on
		a logistic regression model with
		treatment as an independent variable.
Rate of postmeal severe	$\leq 0.5, \leq 1, \leq 2, \leq 4, >1$ to $\leq 2, >2$	Due to limit data for the rare event,
hypoglycemic events (per patient per	to $\leq$ 4 and $>$ 4 hours after start of	only summary statistics will be
year / 100 years) for all 3 main meals	a meal within 0-12,12-26, 0-26	provided by treatment. No statistical
	weeks	comparison will be conducted.
Incidence of postmeal severe	$\leq 0.5, \leq 1, \leq 2, \leq 4, >1$ to $\leq 2, >2$	Fisher exact test will be used for
hypoglycemic events for all 3 main	to $\leq$ 4 and $>$ 4 hours after start of	treatment comparison.
meals	a meal within 0-12, 12-26, 0-	
	26weeks	

Summary of Analyses for Endpoints Related to Hypoglycemia

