#### 6.13.2. Subgroup Analyses for Hypoglycemic Events

For the documented symptomatic hypoglycemia based on the thresholds of blood glucose  $\leq$ 70 mg/dL, the following subgroups will be analyzed using data collected from all randomized patients prior to discontinuation of IP through Week 26:

- age (<40,  $\geq40$  years)
- hemoglobin A1c stratum (≤8.5% vs. >8.5%)
- region
- type of basal insulin during the lead-in period (glargine U-100 vs. degludec U-100)
- prandial insulin dosing plan (carbohydrate counting or pattern adjustment)

The event rate and incidence will be analyzed using the same model specified in Table 6.5 with the addition of factors for subgroup, and 2-way interaction of subgroup and treatment. The 2-way interaction will be used to evaluate treatment by subgroup interaction.

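### The main negative binomial models for hypoglycemia rates leave out all four randomization strata, which costs some precision to the extent that the strata predict hypoglycemia

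*Protocol*

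**What the plan says.** Protocol Section 7.2 and SAP Section 5.3 stratify the 1:1 randomization by four factors. Two are country (China vs. Other) and the Visit 7 HbA1c stratum. The protocol words the remaining two as follows: "type of basal insulin during the lead-in period (glargine U-100 vs. degludec U-100), and use of metformin at study entry (yes vs. no").

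For non-severe hypoglycemia rates, the Protocol (Synopsis and Section 10.3.4) plans negative binomial regression with an exposure offset: "The model will include treatment and the baseline hypoglycemia rate (measured during lead-in) as a covariate". The Revision History of SAP Version 2 changes this: "Removed the baseline rate covariate from all hypoglycemia models as there were many critical outliers". The operative model is therefore the one in SAP Table 6.5, worded for the postmeal rates as "Negative binomial regression with treatment, and log (exposure/30 days or exposure/365.25 days) as the offset in the model". The general rate row of the table lists the same terms.

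On strata, SAP Section 6.2 states: "Other analyses will include the stratification factors as noted in Sections 6.11 and 6.12". Sections 6.11.2 and 6.11.5 put all four into the models for postprandial excursions, 1,5-AG, 10-point SMBG and insulin doses. Table 6.5 puts in none. SAP Section 6.13.2 adds HbA1c stratum, region and "type of basal insulin during the lead-in period (glargine U-100 vs. degludec U-100") to the Table 6.5 models as subgroup factors, for documented symptomatic hypoglycemia at the 70 mg/dL threshold only.

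**The concern.** Stratified allocation balances the arms on the four factors. If those factors also predict the event rate, a model without them leaves the between-stratum differences in the overdispersion term, and the standard error of the log rate ratio is larger than it has to be. The rates of documented symptomatic hypoglycemia, overall and postmeal, belong to named secondary objectives. A wider interval makes a real difference between the insulins harder to see.

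The SAP gives no reason for leaving the strata out. Its reason for removing the lead-in rate, critical outliers, cannot apply to two-level factors fixed before randomized treatment starts. The removal also gives the strata more to do, because the lead-in rate would have absorbed part of any stratum effect.

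**Working it through.** **The plan's own figure.** The only stated precision figure is for HbA1c (Protocol 10.1): margin 0.4, SD 1.1, 149 per arm, 2-sided 95% interval. SE = 1.1 × √(2/149) = 0.1274, and power = Φ(0.4/0.1274 − 1.96) = Φ(1.18) = 88.1% (87.9% with the noncentral t), against 87% stated. With 15% dropout, 298/0.85 gives 351, against 350. These reproduce. The documents give no event rate, dispersion or stratum effect for hypoglycemia, so everything below rests on assumptions.

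**Set-up.** 350 patients, 1:1 within strata, 15% leaving early. Counts are gamma-Poisson with dispersion k and a log-exposure offset, fitted by maximum likelihood with 100 to 150 replicates per setting. Excess width on the log scale = SE(treatment only) / SE(treatment + strata) − 1.

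**Two prognostic strata** (basal type with an assumed 30% share, HbA1c stratum with an assumed 50%). Each cell gives the SE without and with strata, then the excess from unrounded SEs.

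| Events/patient-year, k | Stratum ratio 1.25 | 1.5 | 2.0 |
|---|---|---|---|
| 4, 1.0 | 0.1347 / 0.1337: 0.8% | 0.1371 / 0.1337: 2.5% | 0.1465 / 0.1367: 7.2% |
| 20, 0.5 | 0.0852 / 0.0837: 1.8% | 0.0888 / 0.0839: 5.7% | 0.0982 / 0.0852: 15.3% |
| 20, 1.0 | 0.1135 / 0.1126: 0.9% | 0.1156 / 0.1124: 2.8% | 0.1238 / 0.1145: 8.2% |
| 20, 2.0 | 0.1554 / 0.1552: 0.1% | 0.1589 / 0.1566: 1.5% | 0.1640 / 0.1563: 4.9% |

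At a stratum ratio of 1.0 the excess lies between −0.2% and 0.2%, which is simulation noise.

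**Four equally prognostic strata**, 20 events per patient-year, k = 1.

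| Model without strata | Ratio 1.0 | 1.25 | 1.5 | 2.0 |
|---|---|---|---|---|
| SAP Version 2 (treatment only) | 0.1% | 1.8% | 5.3% | 15.4% |
| Protocol (lead-in rate kept) | 0.2% | 1.0% | 2.7% | 6.9% |

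**What this is worth.** Required sample size scales with the squared width. 1.018² = 1.036, 1.053² = 1.109 and 1.154² = 1.332, so the four-strata losses under the SAP model correspond to about 4%, 11% and 33% more patients. For a mid-range case (two strata, 20 events per year, k = 1, ratio 1.5) and an observed rate ratio of 1, the 95% limits are exp(±1.96 × 0.1156) = 0.797 to 1.254 without strata, and exp(±1.96 × 0.1124) = 0.802 to 1.246 with them.

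**Cross-check.** A moment formula multiplies (1/μ + k_u) by Σ w_c/(1/μ_c + k) and takes the square root, with k_u = (1 + k)·m₂/m₁² − 1, where m₁ and m₂ are the first two moments of the stratum multiplier. With μ = 10 events, k = 1, four strata and assumed shares of 20, 50, 30 and 10%, it gives 3.3%, 11.4% and 35.4% at ratios 1.25, 1.5 and 2.0. It is higher because it charges the whole between-stratum variance to the treatment-only model, as if allocation had not been stratified. The simulated figures compare the standard errors that the planned fit would report, so the conclusion uses those.

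**The case against.** The strongest reply is that the omission follows a convention. Hypoglycemia is analysed as a safety measure, SAP 6.2 ties the stratification factors to efficacy models, and the main models for liver tests, laboratory values, vital signs and antibody level also omit strata. That explains the pattern, but it does not show any harm in adjusting.

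Several stronger readings are tempting, and the documents do not support them:

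- That the intervals are wider, without condition. Nothing in either document shows that any stratum predicts hypoglycemia. A subgroup list looks for effect modification, and Section 6.13.2 omits metformin and names region, not China vs. Other.
- That the strata never enter a hypoglycemia model. Section 6.13.2 fits three such factors, one at a time, with interaction.
- That the pointer in SAP 6.2 to Section 6.12 is empty. The antibody-status subgroup analyses in 6.12.7.1 borrow Section 6.11 models that carry strata.
- That every hypoglycemia objective is affected. For severe events, "The rate of severe hypoglycemia per 100 years will be compared between treatment groups using the empirical method". Incidence uses "Logistic regression with treatment as an independent variable", where adding strata would change the odds ratio being estimated.

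Two further objections stand in part. The postmeal rates alone make 7 windows × 3 periods × 2 thresholds = 42 models, some likely sparse, so a fallback rule may leave different covariates in parallel rows. And dropping the lead-in rate may cost more than omitting the strata: 9 to 17% wider in the four-strata setting, assuming about half of the patient heterogeneity is shared between lead-in and treatment. That is a separate matter and does not remove this one.

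**Conclusion.** The point holds in a limited form. The main Table 6.5 rate models use none of the four factors on which patients were randomized, and no reason is given. The cost is conditional: about 0% excess interval width if the strata do not predict hypoglycemia, roughly 0 to 6% for stratum rate ratios of 1.25 to 1.5, and 5 to 15% at 2.0. These figures rest on assumed rates of 4 to 20 events per patient-year, dispersion of 0.5 to 2 and assumed stratum shares and effects.

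The severity is minor. A reader might infer a biased rate ratio or a type I error problem, but the documents support neither. These endpoints are also outside the graphical testing procedure (SAP 6.5), and the primary HbA1c conclusion is untouched.

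**What to change.** Before unblinding, add country (China vs. Other), HbA1c stratum, type of basal insulin and metformin use as fixed effects to every negative binomial rate model in SAP Table 6.5. State which HbA1c value defines the stratum, since SAP 5.3 says Visit 7 and SAP 6.2 says baseline. Prespecify a fallback to the treatment-only model for any category that does not converge, and report where it was used. With a log link and no treatment-by-stratum interaction, the rate ratio being estimated stays the same. Leave the severe-event comparison and the logistic incidence models as they are.

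If the study is already unblinded, keep Table 6.5 as the main analysis and report the stratum-adjusted model as a labelled sensitivity analysis. If the sponsor prefers to leave the strata out, one sentence of justification in the SAP would do.

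The cost is a few lines of SAP text, up to four degrees of freedom, and possibly different covariates in sparse categories. Rate and incidence for the same objective would also then be adjusted differently.
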